## Purpose of the Study

The purpose of this study is to develop a multiplexed low coherence interferometry (mLCI) endoscopic probe for mapping the epithelial types of the cervix. This vaginal mLCI probe will obtain optical measurements from the cervix. These measurements can be used to create a map of the surface cells that distinguishes ectocervical epithelia, endocervical epithelia, and the squamocolumnar junction (t-zone) between them, which is the region where cervical dysplasia is most likely to occur.

The research study described here will be a preliminary study to evaluate the performance of the mLCI device for detection of cervical dysplasia. The results from a small study at Duke will help to optimize the function of the mLCI instrument before completing a larger study with collaborators at Jacobi Medical Center (see *Background & Significance* below). The device will be studied in a larger subject population at Jacobi to determine how effectively it can distinguish the types of cervical epithelia.

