### **Study Procedures for subjects at Jacobi**

Subjects will be informed of the study when they present to the clinic for a regular clinical care visit. If interested in participating, subjects will complete the following study-related procedures in addition to the standard of care visit procedures.

- Read consent form
- Ask / answer questions
- Sign consent form
- Urine pregnancy test – must be negative before imaging can occur
- Colpophotography of cervix to compare with mLCI data
- mLCI examination of the cervix (with speculum)

We will obtain written informed consent and confirm eligibility criteria. Data collection will include a brief medical history and pregnancy testing.

The doctor will then insert a speculum in order to directly visualize the cervix. Colpophotographs will be taken to compare to mLCI data during data analysis. The doctor will then gently place the mLCI probe against the cervix. White light camera visualization, incorporated into the mLCI probe, will guide the probe positioning by the clinician to confirm contact with the cervical epithelium. The probe will then be held in place for mLCI data acquisition for up to 1 minute. When data collection is completed, the mLCI probe will be removed and placed on a custom holder that prevents the contact portions of the probe from coming into contact with contaminating surfaces.

The doctor will then continue with the rest of the patient's standard of care visit procedures.

At some visits, the physician may choose to make an additional measurement with the mLCI device, by inserting it without a speculum and using the white light camera (incorporated into the mLCI probe) for visual guidance to position the probe. Comparing measurements made by inserting the mLCI device with and without a speculum will allow us to determine if the white light visualization by the camera is sufficient to correctly place the probe over the cervix without having to use a speculum in future studies.

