### **Selection of Subjects at Jacobi**

We do not have any role in selection of the research subjects at Jacobi: this is the responsibility of that site.

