### ***Data analysis for Jacobi site***

Construction of epithelium maps by mLCI: Maps of the cervix delineating the T-zone will be created from each subject's mLCI data. The extent of columnar and squamous epithelia will be reported as a percentage of the image of the epithelium. Each scan in the 36 point field will initially be reviewed manually to determine the epithelium type based on the depth-resolved reflection profile for that point. The presence of clear histological layers is indicative of squamous epithelium while a thinner layer with less structure indicates columnar epithelium [22]. As we compile a database of mLCI maps of the cervix, we will develop automated algorithms for assessing epithelial types and transitions by using cluster analysis to discriminate scans. The mLCI maps will be compared to digital colposcopy analysis to assess accuracy.

Measurement of epithelial areas by colposcopy: Digital colposcopic images will be viewed in Adobe Photoshop for quantitative computerized planimetry as previously published [23, 24]. We will manually outline all areas of columnar, metaplastic and squamous epithelia and the total visible cervical face. Total pixel counts of the various epithelial types will be calculated and ectopy expressed as percentage of the total cervix.

Correlation of mLCI images to colposcopy and detailed written maps: The mLCI epithelial maps will be visually compared to colposcopic images to achieve co-registration. This is feasible based on the relatively modest number of patients in the study. The written map and white light imaging via the probe will aid in coregistration. We will correlate mLCI readings with calculated areas of epithelial types (pixel counts and percentage). Biostatistical analyses will address covariates including age, infections, cytology, menstrual cycle, and sexual behaviors.

Potential problems, alternative strategies, and benchmarks for success: The mLCI approach will be viewed as successful if there is less than average absolute difference of 10% in the area estimate compared with manual analysis.

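### The Jacobi 10% success rule has no no-information comparator, so a map that assigns every woman the same columnar share could meet it

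*Combined protocol and SAP*

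**What the plan says.** The Purpose of the Study gives the aim of the Jacobi part as "to determine how effectively it can distinguish the types of cervical epithelia".

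Under Data analysis for Jacobi site, the mLCI side of the comparison is defined thus: "The extent of columnar and squamous epithelia will be reported as a percentage of the image of the epithelium". The colposcopy side is: "Total pixel counts of the various epithelial types will be calculated and ectopy expressed as percentage of the total cervix". The reference has three tissue classes: "We will manually outline all areas of columnar, metaplastic and squamous epithelia and the total visible cervical face". The same section closes with the benchmark: "The mLCI approach will be viewed as successful if there is less than average absolute difference of 10% in the area estimate". The reference for that difference is given only as a manual analysis. The text does not say whether the 10% is absolute or relative, or which tissue's area is meant.

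On who is measured, Selection of Subjects at Jacobi says: "We do not have any role in selection of the research subjects at Jacobi: this is the responsibility of that site". The Multi-site Study section sets a target of 40 completers from at most 100 enrolled, with no condition on what tissue is visible. The Jacobi procedures provide the reference image: "Colpophotographs will be taken to compare to mLCI data during data analysis".

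The analysis section also plans visual co-registration, correlation of mLCI readings with colposcopic areas, and covariate analyses. None of these is part of the success rule.

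**The concern.** Distinguishing two tissue types can be shown only where both are present, and only by doing better than a guess that ignores the optical data. An average error in area share tests neither. In a woman with little columnar tissue on the cervical face, calling everything squamous is nearly right by default. Where women have similar amounts of columnar tissue, giving all of them the same typical share is nearly right too.

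The benchmark is a fixed number averaged over all women, so how demanding it is depends on the case mix. The plan neither describes that mix nor adjusts for it. At stake is what a pass would mean: it might be reported as evidence of discrimination when an uninformative map would have passed on the same women.

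**Working it through.** **Inputs from the documents.** Threshold 10%; 40 completers; enrolment cap 100; 36 measurement locations (mLCI instrument section). One location is 100/36 = 2.78% of the map, and 10% is 3.6 locations. The plan gives no expected columnar share, standard deviation or derivation of the 40, so it has no figure to reproduce. Every distribution below is an assumption.

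**Step 1: the all-squamous map.** Let e_i be woman i's reference columnar share in percentage points. The map estimates 0, so her absolute difference is |0 − e_i| = e_i. The average is mean(e), and the map passes exactly when mean(e) < 10. If a fraction f of women have any columnar tissue, their mean may be as high as 10/f: 20% for f = 0.5, and 40% for f = 0.25.

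Assumed mixtures, with pass rates from simulated cohorts of 40:

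| Women with none | Range in the rest (uniform) | Score of all-squamous map | Cohorts in which it passes |
|---|---|---|---|
| 50% | 5–30% | 0.5 × 17.5 = 8.75 | about 79% |
| 70% | 5–30% | 0.3 × 17.5 = 5.25 | over 99% |
| 70% | 10–50% | 0.3 × 30 = 9.0 | about 66–67% |
| 50% | 10–50% | 0.5 × 30 = 15 | about 3% |

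With smooth (Beta) distributions and 40 women, the pass probability is 0.999 at mean 5% (SD 8), 0.52 at mean 10% (SD 10) and 0.002 at mean 15% (SD 12).

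**Step 2: any constant map.** A map giving every woman share c scores mean|e_i − c| and passes when that is below 10. This score is smallest when c is the median.

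- Uniform 5–30%, c = 17.5: 12.5/2 = 6.25 points, a pass. The all-squamous map scores 17.5 on the same women and fails.
- The same range on the real grid, 6 of 36 locations (16.7%): (11.67² + 13.33²)/(2 × 25) = 6.28 points, a pass.
- Uniform 5–30%, a poorly chosen c = 10: (5² + 20²)/(2 × 25) = 8.5 points, still below 10.
- Beta with mean 15% (SD 12), c at the median of 12.0%: 9.2 points, passing in about 75% of cohorts.
- Beta with mean 20% (SD 15), c at the median of 16.7%: 11.8 points, passing in about 13%.

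A comparison with the all-squamous map alone would therefore be too weak. The best constant is the relevant comparator.

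**Step 3: other readings of the 10%.**

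- Relative to squamous area: the all-squamous error is e/(1 − e). If every woman has the same share, it passes below 9.1%.
- Relative to columnar area: its error is 100% in any woman with columnar tissue, so it fails. The measure is undefined in women with none.
- Metaplastic area counted as non-squamous: columnar plus metaplastic together must average below 10 points for the all-squamous map to pass.

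**The case against.** Four points against the concern have force.

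- **Eligibility.** A reader might infer that Jacobi enrols women regardless of visible columnar tissue. The documents do not show that. The Jacobi procedures refer to confirming eligibility criteria, but those criteria belong to the site and are not in this protocol. All that can be said is that this protocol states none.
- **Case mix.** A reader might infer that the cohort will have little ectopy. Nothing supports that either. The Background describes a patient population spanning all states of cervical health, healthy young women among them, and stresses mixed and transitional epithelium. The pass rates for the assumed mixtures run from 3% to over 99%, which shows dependence on case mix, not likelihood.
- **Unit.** The weakness is not independent of how the measure is defined. If the 10% is relative to columnar area, the all-squamous map cannot pass in a cohort where columnar tissue is present. Percentage points is the natural reading, since both areas are reported as percentages, but the text does not settle it. Manual analysis most naturally means the colposcopic outlines, though it could mean manual reading of the mLCI scans. The same algebra would then apply to that reference.
- **Other analyses.** The planned correlation would expose a constant map, which has no variance. That is true and useful, but the rule can be met whatever the correlation shows.

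The study is also described as preliminary, and no text makes the benchmark a formal gate for later work.

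**Conclusion.** The concern holds as a gap in the success rule. Under the percentage-point reading, the all-squamous map passes if and only if the cohort's mean columnar share is below 10 points. A constant map passes if and only if the average absolute deviation around its constant is below 10 points. Both statements are exact. How often either would happen at Jacobi is unknown, because the documents give no ectopy distribution.

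It would go too far to say that a pass or fail depends only on how much ectopy the clinic sees. That is true of a map carrying no information, not of a device that does discriminate. It would also go too far to restrict the 40 to women with a visible junction. If 70% had none, 100 enrolled women would yield 30 on average even if all completed. Counting them during enrolment would also need an image read that the plan places in data analysis. The defect can be repaired in the analysis.

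**What to change.** 1. State that the 10% is in percentage points of columnar area, that the reference is the manual colposcopic outline, and how metaplastic area is classed.
2. Declare success only if the mLCI average absolute difference is below 10 points **and** below that of the best constant map scored on the same women. The candidates are all-squamous and the cohort's median columnar share. The median minimises average absolute error, so beating it also beats all-squamous.
3. Report the result separately for women with and without columnar epithelium visible on the colpophotograph already taken.
4. Report per-point agreement on the co-registered 36-point maps as supporting evidence, since a correct share can come from wrongly placed points.
5. Leave enrolment and the count of 40 unchanged.

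The cost is a few lines of analysis on data already collected. The downside is that the benchmark becomes harder to pass, and a cohort with little ectopy may be inconclusive on discrimination. In the extreme, if no woman had columnar tissue, the all-squamous map would score 0 and could not be beaten. Inconclusive would then be the accurate description of what had been learned about discrimination.

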### **Multi-site Study: Responsibilities**

[name], the Duke PI of this study, is the primary awardee of the NIH grant supporting this work. [name] and his team have developed the mLCI research device and will conduct a small study at Duke (described below) to assess if any adjustments to the device are needed before it is sent to Jacobi Medical Center for the larger study. The study at Jacobi Medical Center will be funded as a subaward / consortium agreement of [name] NIH grant. The research proposed in this study protocol addresses Specific Aim 1 of the NIH grant.

Duke will recruit up to 15 women to enroll in this study, in order to achieve the target number of 10 subjects who complete the study at that site. Jacobi will enroll up to 100 women for this study, in order to achieve the target number of 40 women who complete the study at that site. Data from both sites will be analyzed at Duke. Data received from Jacobi will be de-identified before being sent to Duke. Study conduct at Duke will be under the oversight of the IRB of the Duke University Health System. Study conduct at Jacobi Medical Center will be under the oversight of the IRB of the Albert Einstein College of Medicine and Montefiore Medical Center.

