## **Data Analysis & Statistical Considerations**

### ***Data analysis for Duke site***

The proposed study is designed as a pilot study, intended to provide feasibility and usability data to inform future studies on a larger scale. The planned pilot study will include 10 subjects, which will yield success/failure metrics of the probe design with 10% precision. Elements of the probe performance that will be evaluated include ease of use by the medical practitioner, patient comfort, ability to access the relevant anatomy, and quality of mLCI imaging data. Because the goal of the pilot study is the evaluation of general feasibility, no subject data will be excluded if no predetermined exclusion criteria are met.

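### The Jacobi benchmark judges success on a bare sample mean, so a device whose true average error is at or slightly above 10% has a substantial chance of being called successful

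*Combined protocol and SAP*

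**What the plan says.** Under Data analysis for Jacobi site, the area estimates are to be checked against planimetry of colposcopic images: "The mLCI maps will be compared to digital colposcopy analysis to assess accuracy". The section ends with one numerical benchmark: the approach "will be viewed as successful if there is less than average absolute difference of 10% in the area estimate" relative to manual analysis. It does not say whether 10% means percentage points or a relative difference, which epithelial area it covers, or which women are analysed.

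The number of women comes from Multi-site Study: Responsibilities, which sets an enrolment ceiling ("Jacobi will enroll up to 100 women for this study") and ties it to a completion target ("in order to achieve the target number of 40 women who complete the study at that site"). No reason is given for 40. The only other statistical sentence for this site concerns covariates: "Biostatistical analyses will address covariates including age, infections, cytology, menstrual cycle, and sexual behaviors". The one precision statement in the document belongs to Duke and to a different kind of outcome: "The planned pilot study will include 10 subjects, which will yield success/failure metrics of the probe design with 10% precision".

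Purpose of the Study calls the research preliminary, and Potential Benefits describes early feasibility work. Of the Jacobi part, however, Purpose of the Study says: "The device will be studied in a larger subject population at Jacobi to determine how effectively it can distinguish the types of cervical epithelia".

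**The concern.** The benchmark treats the observed mean as though it were the device's true average error. With about 40 women the mean carries sampling error of a few points, so a result just under 10 is compatible with a true error on either side of the line. The plan would report both cases with the same word.

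A mean is also silent about spread between women. The aim is to map each woman's cervix, and an acceptable average can coexist with a minority of maps that are badly wrong.

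At stake is how the main Jacobi result is read. It is the only numerical success criterion for the larger site, and a reader could not tell a secure result from a marginal one.

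**Working it through.** **Inputs from the plan.** Cut-off 10; target n = 40 completers. The plan gives no SD, expected error, alpha, power or confidence level for Jacobi, so 40 cannot be reproduced from stated inputs.

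**Assumptions.** The woman is the unit, and 10% is read as percentage points. The SD of the per-woman absolute difference is taken over 4 to 15 points. Two error shapes are also used: half-normal (a mean of 10 implies an SD of about 7.6) and exponential (a mean of 10 implies an SD of 10).

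**Step 1: precision of the mean.** SE = SD/√40. At SD 7.5, SE = 7.5/6.325 = 1.19, and the 95% half-width is 2.023 × 1.19 = 2.4 points. Over SD 4 to 15 the half-width runs from 1.3 to 4.8 points.

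**Step 2: chance of passing the rule as written.** By normal approximation, P(success) = Φ((10 − μ)/SE). For example, at SD 7.5 and μ = 11, Φ(−1/1.19) = 0.20. At μ = 10 the numerator is zero, so the result is 50% for any SD. The last two rows are simulations of 100,000 trials each.

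| Assumption | True 10 | 11 | 12 | 13 | 15 |
|---|---|---|---|---|---|
| SD 4 | 50% | 5.7% | 0.1% | 0.0% | 0.0% |
| SD 7.5 | 50% | 20% | 4.6% | 0.6% | 0.0% |
| SD 10 | 50% | 26% | 10% | 2.9% | 0.1% |
| SD 15 | 50% | 34% | 20% | 10% | 1.8% |
| Half-normal | 51% | 23% | 7.8% | 2.2% | 0.1% |
| Exponential | 52% | 29% | 14% | 6.2% | 0.9% |

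A second simulation of 60,000 trials per scenario gave 29.7% for exponential errors at 11, hence the quoted range of 23-30%.

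**Step 3: what the mean can hide.** This is an invented illustration. If 32 women differ by 3 points and 8 by 35, the mean is (32×3 + 8×35)/40 = 9.4, which meets the benchmark although one woman in five is badly wrong. The SD is 32 × √(0.2 × 0.8 × 40/39) = 13.0 and the SE is 2.05. The 95% interval is 9.4 ± 2.023 × 2.05, about 5.3 to 13.5.

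**Step 4: what an upper-limit criterion would do.** The simulated chance that a t upper limit falls below 10:

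| Limit | True 8 | True 10 | True 11 |
|---|---|---|---|
| One-sided 95% | 50-65% | 7-9% | 1-3% |
| Upper end of two-sided 95% | 41-54% | 4-6% | 1-2% |
| Rule as written | 94-98% | 51-52% | 23-30% |

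The one-sided 95% limit passes 7-9% at a true error of 10 rather than the nominal 5%, because absolute errors are skewed. To clear that limit, the observed mean must be at most 10/(1 + 1.685 × CV/√40). That is 8.3 for half-normal errors (CV 0.756) and 7.9 for exponential errors (CV 1).

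**The case against.** - **Any cut-off behaves this way at its own boundary.** A rule that compares a sample mean with 10 passes about half the time at 10, and a stricter rule moves that point to a lower true error. A device truly at 8, inside the plan's own target, would earn success only 50-65% of the time under a one-sided 95% limit. This stands: imposing the limit as the sole criterion is a trade of false success against false failure, not a plain correction.
- **This is early feasibility work.** The plan describes it so and attaches no hypothesis test or go/no-go consequence to the benchmark. This also stands, and it lowers the weight of the point. It does not justify omitting an interval, because the Jacobi part is meant to show how effectively the device works and the plan attaches a success verdict to one number.
- **The numbers rest on an assumed spread.** This is true of every figure above the boundary, which is why ranges are shown. Only the 50% at a true error of 10 is free of the SD, by normal approximation.
- **The mean is not the only analysis.** Per-subject maps, visual comparison with colposcopy and correlation with calculated areas are also planned, so gross mismatches need not go unseen. None of these, however, is tied to the benchmark or summarises how many women are badly mapped.

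A reader might infer that the rule often passes failing devices in general, or that a failing device would go forward as validated. The documents do not support either. Pass rates fall to 2-6% at a true error of 13 under the two simulated shapes and to 2% or less at 15 over the whole SD range. The plan makes no validation claim.

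**Conclusion.** The point holds near the benchmark. The plan would call mLCI successful on a mean with no stated uncertainty, so a device at or slightly above a true average error of 10 has a substantial chance of that verdict. The chance is about 50% at 10. It is 23-30% at 11 and 8-14% at 12 if absolute errors are half-normal to exponential, or 6-34% and 0.1-20% over an SD of 4 to 15. The rule does reject clearly poor devices.

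These sizes assume 40 analysed women and a percentage-point scale. On a relative scale the 50% at the benchmark carries over, but the other figures would depend on the spread in those units. That the mean does not show the number of badly mapped women needs no SD assumption. This is a worthwhile, inexpensive improvement to the analysis text, not a fatal flaw.

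**What to change.** Keep 10% as a descriptive feasibility benchmark and add a paragraph to Data analysis for Jacobi site that does the following:

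- State that the woman is the unit, whether 10% means percentage points, which epithelial area it covers and which women are analysed.
- Report the average absolute difference with a 95% interval, by bootstrap over women.
- Describe the benchmark as 'met with confidence' only if the upper limit is below 10%, and as 'met on the point estimate only' if the mean is below 10% but the limit is not. Say whether that limit is one-sided 95% or the upper end of the two-sided interval.
- Report beside it the share of women within 10 points, with an exact interval, and the 90th percentile of the absolute difference.

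Making the upper limit the sole success criterion is optional. If it is chosen, the plan should acknowledge the 50-65% pass rate for a device truly at 8 and the roughly 7-9% false success at 10 (both for the one-sided 95% limit).

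The cost is a little more analysis and no new patients, data or procedures. The downside is that a mean just below 10% can no longer be reported as unqualified success.
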